# **13. TRIAL MANAGEMENT**

# **13.1** Data and Safety Monitoring Plan (DSMP)

The study will be conducted in accordance with the University of Illinois Cancer Center's Data and Safety Monitoring Plan (DSMP). The University of Illinois Cancer Center Data Safety and Monitoring Committee (DSMC) will review and make recommendations on this trial. BTCRC AHQ will provide the University of Illinois Cancer Center DSMC with periodic data reports to comply with the UICC DSMC review requirements.

In addition, BTCRC AHQ oversight activities include:

- Review of all adverse events requiring expedited reporting as defined in the protocol.
- Provide trial accrual progress, safety information, and data summary reports to the sponsor-investigator.
- Submit data summary reports to the lead institution DSMC for review as per their DSMP.

# 13.2 University of Illinois Cancer Center Data Safety Monitoring Committee

BTCRC AHQ will provide the UICC DSMC with the following:

- Adverse event summary report
- Audit results, if applicable
- Data related to stopping/decision rules described in study design
- Study accrual patterns
- Protocol deviations

The University of Illinois Cancer Center DSMC will review study data every quarter. Documentation of DSMC reviews will be provided to the sponsor-investigator and BTCRC AHQ. Issues of immediate concern by the DSMC will be brought to the attention of the sponsor-investigator and other regulatory bodies as appropriate. The sponsor-investigator will work with BTCRC AHQ to address the DSMC's concerns.

#### **13.3** Data Quality Oversight Activities

Remote validation of the EDC system data will be completed on a continual basis throughout the life cycle of the study. A summary report (QC Report) of these checks together with any queries resulting from manual review of the eCRFs will be generated for each site and transmitted to the site and the site monitor. Corrections will be made by the study site personnel.

Monitoring visits to the trial sites may be made periodically during the trial to ensure key aspects of the protocol are followed. Additional for-cause visits may occur as necessary. Source documents will be reviewed for verification of agreement with data entered into the EDC system. It is important for the site investigator and their relevant personnel to be available for a sufficient amount of time during the

monitoring visits or audit, if applicable. The site investigator and institution guarantee access to source documents by BTCRC AHQ or its designee.

The trial site may also be subject to quality assurance audit by Pfizer, AbbVie, or their designee as well as inspection by appropriate regulatory agencies.

# **13.4** Compliance with Trial Registration and Results Posting Requirements

Under the terms of the Food and Drug Administration Modernization Act (FDAMA) and the Food and Drug Administration Amendments Act (FDAAA), the sponsor-investigator of the trial is solely responsible for determining whether the trial and its results are subject to the requirements for submission to the Clinical Trials Data Bank, http://www.clinicaltrials.gov. The sponsor-investigator has delegated responsibility to BTCRC AHQ for registering the trial and posting the results on clinicaltrials.gov. Information posted will allow subjects to identify potentially appropriate trials for their disease conditions and pursue participation by calling a central contact number for further information on appropriate trial locations and study site contact information.

# 14. DATA HANDLING AND RECORD KEEPING

# 14.1 Data Management

BTCRC AHQ will serve as the Clinical Research Organization for this trial. Data will be collected through a web based clinical research platform compliant with Good Clinical Practices and Federal Rules and Regulations. Other study institutions will be given a password to directly enter their own data onto the web site via electronic case report forms (eCRFs). BTCRC AHQ personnel will coordinate and manage data for quality control assurance and integrity.

All data will be collected and entered into the EDC system by study site personnel from participating institutions.

#### 14.2 Case Report Forms and Submission

An electronic case report form (eCRF) is required and must be completed for each included subject. The completed dataset is housed at BTCRC AHQ and is the sole property of the sponsor-investigator's institution. It should not be made available in any form to third parties, except for authorized representatives of appropriate Health/Regulatory Authorities, without permission from the sponsor-investigator and BTCRC AHQ. After the initial publication, the complete data set will be available to all BTCRC institutions.

#### 14.3 Record Retention

To enable evaluations and/or audits from Health Authorities/BTCRC AHQ, the investigator agrees to keep records, including the identity of all participating subjects (sufficient information to link records; e.g., hospital records), all original signed informed consent forms, copies of all source documents, and detailed records of drug disposition. To comply with international regulations, the records should be retained by the investigator in compliance with regulations.

During data entry, range and missing data checks will be performed on-line. The checks to be performed will be documented in the Data Monitoring Plan for the study. A summary report (QC Report) of these

checks together with any queries resulting from manual review of the eCRFs will be generated for each site and transmitted to the site and the site monitor. Corrections will be made by the study site personnel. This will be done on an ongoing basis.

# 14.4 Confidentiality

There is a slight risk of loss of confidentiality of subject information. All records identifying the subjects will be kept confidential and, to the extent permitted by the applicable laws and/or regulations, will not be made publicly available. Information collected will be maintained on secure, password protected electronic systems. Paper files that contain personal information will be kept in locked and secure locations only accessible to the study site personnel.

Subjects will be informed in writing that some organizations including the sponsor-investigator and his/her research associates, BTCRC AHQ, Pfizer, AbbVie, IRB, or government agencies, like the FDA, may inspect their medical records to verify the information collected, and that all personal information made available for inspection will be handled in strictest confidence and in accordance with local data protection laws.

If the results of the study are published, the subjects's identity will remain confidential.

# **15. ETHICS**

# 15.1 Institutional Review Board (IRB) Approval

The final study protocol, including the final version of the informed consent form, must be approved in writing by an IRB. The investigator must submit written approval by the IRB to the BTCRC AHQ office before he or she can enroll any subject into the study.

The site investigator is responsible for informing the IRB of any amendment to the protocol in accordance with local requirements. In addition, the IRB must approve all advertising used to recruit subjects for the study. The protocol must be re-approved by the IRB annually, as local regulations require.

Progress reports and notifications of serious unexpected adverse drug reactions will be provided to the IRB according to local regulations and guidelines.

# **15.2** Ethical Conduct of the Study

The study will be performed in accordance with ethical principles originating from the Declaration of Helsinki. Conduct of the study will be in compliance with ICH Good Clinical Practice, and with all applicable federal (including 21 CFR parts 56 & 50), state, or local laws.

#### **15.3 Informed Consent Process**

The site investigator will ensure the subject is given full and adequate oral and written information about the nature, purpose, possible risks and benefits of the study. Subjects must also be notified they are free to discontinue from the study at any time. The subject should be given the opportunity to ask questions and allowed time to consider the information provided.

The subject's signed and dated informed consent must be obtained before conducting any procedure specifically for the study. The site investigator must store the original, signed informed consent form. A copy of the signed informed consent form must be given to the subject.

# Appendix I – ECOG Performance Status

ECOG Score	Performance Status			
0	Asymptomatic			
1	Symptomatic, fully ambulatory			
2	Symptomatic, in bed $< 50\%$ of the day			
3	Symptomatic, in bed $> 50\%$ of the day but not bedridden			
4	Bedridden			
5	Dead			

Adapted from ECOG Definitions

Class	Functional Capacity	Objective Assessment		
I	Patients with cardiac disease but without resulting limitations of physical activity. Ordinary physical activity does not cause undue fatigue, palpitation, dyspnea, or anginal pain.	No objective evidence of cardiovascular disease.		
п	Patients with cardiac disease resulting in slight limitation of physical activity. They are comfortable at rest. Ordinary physical activity results in fatigue, palpitation, dyspnea, or anginal pain.	Objective evidence of minimal cardiovascular disease.		
ш	Patients with cardiac disease resulting in marked limitation of physical activity. They are comfortable at rest. Less than ordinary activity causes fatigue, palpitation, dyspnea, or anginal pain.	Objective evidence of moderately severe cardiovascular disease.		
IV	Patients with cardiac disease resulting in inability to carry on any physical activity without discomfort. Symptoms of heart failure or the anginal syndrome may be present even at rest. If any physical activity is undertaken, discomfort is increased.	Objective evidence of severe cardiovascular disease.		

Adapted from the American Heart Association Guidelines

# **Appendix III – Prohibited and Cautionary Medications**

#### **Excluded throughout the study**

**Strong CYP3A inducers** – avasimibe, carbamazepine, enzalutamine, mitotane, phenytoin, rifampin, St. John's wort

Moderate CYP3A inducers - bosentan, efavirenz, etravirine, modafinil, nafcillin

Excluded during ramp-up phase and Cautionary at the Cohort Designated Dose

**Strong CYP3A inhibitors -** boceprevir, clarithromycin, cobicistat, conivaptan, danoprevir/ritonavir, elvitegravir/ritonavir, idelalisib, indinavir, itraconazole, ketoconazole, mibefradil, lopinavir/ritonavir, nefazodone, nelfinavir, ritonavir, paritaprevir/ritonavir combinations, posaconazole, saquinavir, telaprevir, telithromycin, tipranavir/ritonavir, voriconazole

**Moderate CYP3A inhibitors -** amprenavir, aprepitant, atazanavir, cimetidine, ciprofloxacin (*not levofloxacin*), clotrimazole, crizotinib, cyclosporine, darunavir/ritonavir, diltiazem^1, erythromycin, fluconazole (>200mg), fosamprenavir, imatinib, isavuconazole, tofisopam, verapamil

Cautionary

Warfarin

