- 14. Patients who are positive for hepatitis B or C infection with the exception of those with an undetectable viral load within 3 months. Subjects with serologic evidence of prior vaccination to HBV [i.e., HBs Ag-, and anti-HBs+] may participate.
- 15. Active uncontrolled infection or severe systemic infection. Enrollment is possible after control of infection, at discretion of the treating physician.
- 16. Pregnant or breastfeeding (**NOTE:** breast milk cannot be stored for future use while the mother is being treated on study).
- 17. Patients who have received strong and/or moderate CYP3A inducers or inhibitors within 7 days prior to the initiation of study treatment unless deemed necessary by the treating physician. (See Section 5.8.2 and Appendix III)
- 18. Patients who have consumed grapefruit, grapefruit products, Seville oranges (including marmalade containing Seville oranges) or Starfruit within 3 days prior to the initiation of study treatment.
- 19. Malabsorption syndrome or other condition that *precludes* enteral route of administration.
- 20. Psychological, familial, sociological, or geographical condition that would preclude study compliance and follow-up.
- 21. Unable or unwilling to undergo a screening bone marrow study.
- 22. Other severe acute or chronic medical or psychiatric condition, or laboratory abnormality that may increase the risk associated with study participation or investigational product administration or may interfere with the interpretation of study results and, in the judgment of the investigator, would make the patient inappropriate for enrollment in this study.

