# 5.3 Dose Cohorts

# 5.4 Induction (Cycle 1) and Consolidation (Cycle 2):

Cycle 1: Gemtuzumab Ozogamicin (GO) 3 mg/m^2 IV infusion (up to one 4.5 mg vial) will be given on days +1, +4, and +7 in combination with daily oral administration of Venetoclax during Induction. Based on previous studies, Venetoclax dose will start at 200 mg daily with dose escalation planned over 3 cohorts to identify the recommended phase 2 dose (RP2D). Dose cohort 3 will use the maximum dose of Venetoclax of 600 mg orally daily. Because of evidence of tumor lysis syndrome (TLS) with Venetoclax use in previous CLL studies, we will use a 3-day stepwise ramp up in cycle 1 to the target dose for all cohorts (see Table 1). Patients should expect to be hospitalized throughout Induction/Cycle 1, although medically stable patients may be discharged from the hospital under close supervision at the discretion of the treating physician. Patients do not have to be hospitalized during the first week of consolidation if the treating physician wishes to administer Gemtuzumab (C2D1 and D4) in the outpatient clinic.

Day	Cohort 1 (mg)	Cohort 2 (mg)	Cohort 3 (mg)
-2	50	50	100
-1	100	100	200
0	100	200	400
1–28	200	400	600

Table 1. Venetoclax Ramp-up schedule

Clinical and hematological responses will be assessed after the end of both the induction and consolidation cycles. Bone marrow assessment will occur on day 28 regardless of absolute neutrophil count (ANC) or platelet recovery.

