#### Strong CYP3A Inhibitors

Venetoclax is predominantly metabolized by CYP3A4/5 therefore concomitant use with strong CYP3A inhibitors (e.g., ketoconazole, conivaptan, clarithromycin, indinavir, itraconazole, lopinavir, ritonavir, ritonavir-boosted nirmatrelvir [Paxlovid], telaprevir, posaconazole, voriconazole) at initiation should be avoided. If use is deemed medically necessary by the treating physician (recognizing that this may increase the risk of tumor lysis syndrome), see Table 4 for dosing instructions. For patients who have completed the ramp-up phase and are on a steady daily dose of Venetoclax, see Table 4 for steady dose instructions – note that Posaconazole requires greater dose reductions than other strong CYP3A inhibitors. If the strong CYP3A inhibitor is discontinued, resume the Venetoclax dose that was used prior to initiating the CYP3A inhibitor 2 to 3 days after discontinuation.

Cohort	Assigned VEN Daily Dose (mg)	Ramp-up day	VEN dose with Posaconazole Daily Dose (mg)	VEN dose with all other strong CYP3A inhibitors Daily Dose (mg)			
		D-2	10	10			
1	100	D-1	10	10			
-1		D0	10	20			
		Steady dose	20	30			
	200	D-2	10	10			
1		D-1	20	20			
1		D0	30	30			
		Steady dose	40	50			
	400	D-2	10	10			
2		D-1	20	20			
2		D0	50	50			
		Steady dose	70	100			
	600	D-2	20	20			
`		D-1	40	50			
3		D0	70	100			
		Steady dose	100	150			

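### Appendix III bars strong and moderate CYP3A inhibitors during the venetoclax ramp-up without exception, but Section 5.8.2 permits them and Table 4 prints ramp-up doses with the strong ones

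*Combined protocol and SAP*

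**What the plan says.** Four places in the protocol govern CYP3A drugs around the start of venetoclax.

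- **Section 3.2, Exclusion 17** excludes patients who took "strong and/or moderate CYP3A inducers or inhibitors within 7 days prior to the initiation of study treatment unless deemed necessary by the treating physician". The exception covers inducers as well as inhibitors. The item then directs the reader to two places: "See Section 5.8.2 and Appendix III".
- **Section 5.8.2, strong inhibitors**, says to avoid them at initiation, then opens an exception, with the doses to be taken from the table: "If use is deemed medically necessary by the treating physician (recognizing that this may increase the risk of tumor lysis syndrome), see Table 4 for". Table 4 gives D-2, D-1, D0 and steady doses for cohorts -1, 1, 2 and 3, in one column for posaconazole and one for all other strong inhibitors.
- **Section 5.8.2, moderate inhibitors and inducers**, says to avoid moderate inhibitors and, where that is impossible, to cut venetoclax by at least half. It states no ramp-up restriction. Inducers are to be avoided, with no exception and no dosing instruction.
- **Appendix III** lists strong and moderate inducers under "Excluded throughout the study", and strong inhibitors (posaconazole among them) and moderate inhibitors under "Excluded during ramp-up phase and Cautionary at the Cohort Designated Dose". Neither heading carries a physician exception.

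On the ramp-up itself, Section 5.4 says "we will use a 3-day stepwise ramp up in cycle 1 to the target dose for all cohorts (see Table 1"). Table 1 has columns for cohorts 1, 2 and 3 only.

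**The concern.** A site with a patient who needs posaconazole or another strong inhibitor when venetoclax starts finds the combination barred in Appendix III and a day-by-day dose schedule for it in Table 4. Nothing says which text prevails. The same split exists for moderate inhibitors, though without a schedule.

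The ramp-up exists because of tumor lysis, and Section 5.8.2 acknowledges that a strong inhibitor at initiation may raise that risk. The situation is foreseeable: Section 5.9 recommends antifungal prophylaxis during induction, and azoles are discouraged rather than barred there.

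There is also a consequence for the primary endpoint. DLTs are counted by assigned dose level with 3 to 6 patients per level, so how a site handles one such patient could bear on an escalation decision. Table 4 matters for the same reason: if its cells do not follow Table 1 consistently, patients at one assigned level may not be handled on one basis.

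**Working it through.** **1. The rules side by side**

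| Drug class | Exclusion 17 (7 days before treatment) | Section 5.8.2 and Table 4 | Appendix III |
|---|---|---|---|
| Strong inhibitor, ramp-up | Excluded unless physician judges necessary | Avoid; allowed if medically necessary; doses printed for D-2, D-1, D0 | Excluded, no exception |
| Moderate inhibitor, ramp-up | Same exception | Avoid; if unavoidable, cut venetoclax by at least 50%; ramp-up not restricted | Excluded, no exception |
| Strong or moderate inducer | Same exception | Avoid; no exception, no dosing | Excluded throughout, no exception |

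Rows 1 and 2 contradict directly for on-study use. Row 3 collides only when a patient admitted under the exception continues the inducer.

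**2. Table 4 against Table 1, posaconazole column**

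Inputs are the Table 1 doses for cohorts 1 to 3 (12 cells) and the cohort -1 assigned dose of 100 mg (1 cell): 13 cells with a known unadjusted dose. The three cohort -1 ramp-up cells cannot be checked, because Table 1 has no such column.

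| Unadjusted dose | Table 4 dose with posaconazole |
|---|---|
| 50 mg | 10 mg (cohorts 1 and 2, D-2) |
| 100 mg | 20 mg (cohort 1 D-1; cohort 2 D-1; cohort 3 D-2; cohort -1 steady); **30 mg (cohort 1 D0)** |
| 200 mg | 40 mg (cohort 1 steady; cohort 3 D-1); **50 mg (cohort 2 D0)** |
| 400 mg | 70 mg (cohort 2 steady; cohort 3 D0) |
| 600 mg | 100 mg (cohort 3 steady; no comparator) |

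Two cells stand apart, each by 10 mg: 30/20 = 1.5 and 50/40 = 1.25 times the other cells for the same unadjusted dose. In cohort 1, Table 1 gives 100 mg on both D-1 and D0, but Table 4 moves from 20 to 30 mg.

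**3. Could rounding explain the differences?**

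The tablets supplied are 10, 50 and 100 mg (Section 10.1.2) and must not be broken (Table 2 footnote), so adjusted doses come in 10 mg steps. The fractions below are a test of compatibility; the protocol states no fraction.

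- *Posaconazole, one-sixth rounded up to 10 mg:* 50/6 = 8.3 → 10; 100/6 = 16.7 → 20; 200/6 = 33.3 → 40; 400/6 = 66.7 → 70; 600/6 = 100. This fits 11 of the 13 cells. The exceptions are the two cells above.
- *Other strong inhibitors, one-quarter to the nearest 10 mg:* 50/4 = 12.5 → 10; 100/4 = 25 → 20 or 30, a tie; 200/4 = 50; 400/4 = 100; 600/4 = 150. This fits all 13, including 100 mg printed as 20 mg in three cells and 30 mg in two.

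**4. Size of the last ramp-up step (D0 to steady dose)**

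- Without an inhibitor: 200/100 = 2.0 (cohort 1), 400/200 = 2.0 (cohort 2), 600/400 = 1.5 (cohort 3).
- With posaconazole: 40/30 = 1.33, 70/50 = 1.4, 100/70 = 1.43.

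**The case against.** The best reply is that most of this can be read consistently, and on several points it succeeds.

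- *A reader might infer that a patient on posaconazole is ineligible under Appendix III.* The documents do not support that. Appendix III is a concomitant-medication list; eligibility is set by Exclusion 17, which contains the physician exception and agrees with Section 5.8.2 on inhibitors. What Appendix III bars is use of the drug during ramp-up.
- *A reader might infer that Exclusion 17 and Appendix III always conflict on inducers.* They cover different windows. A patient who took a necessary inducer five days before treatment and then stopped satisfies both. The absence of inducer dosing is also unremarkable if on-study use is excluded. The collision is confined to continued need.
- *A reader might infer that Table 4 is inconsistent throughout,* because the posaconazole steady doses are 20/100 = 20%, 40/200 = 20%, 70/400 = 17.5% and 100/600 = 16.7% of the assigned dose. All four fit one fraction plus rounding, as does the whole column for other strong inhibitors. Nor does the protocol say Table 4 is a fixed fraction of Table 1; it cites sources not available here. The two odd cells may therefore be deliberate.
- *A reader might infer that posaconazole makes the ramp-up steeper,* because D0 is 30/40 = 75% and 50/70 = 71% of steady dose in cohorts 1 and 2, against 50% without an inhibitor. Those higher fractions mean a smaller final step, not a larger one. In cohort 3 the fraction barely changes (70/100 = 70% against 400/600 = 67%).
- *On cohort -1,* Section 5.4 also speaks of escalation over three cohorts, so its reference to every cohort may mean those three, and cohort -1 is a contingency level. That softens the point, but Table 4 still prints a cohort -1 ramp-up for patients on inhibitors while no table gives one for patients without.
- *On consequences,* Sections 5.8.1 and 5.9 steer sites to non-azole antifungals, so few patients may be affected.

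None of this removes the contradiction between Appendix III and Section 5.8.2 with Table 4.

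**Conclusion.** The concern holds in a limited form. Appendix III and Section 5.8.2 cannot both be followed for a strong or moderate CYP3A inhibitor during ramp-up, and for strong inhibitors Table 4 supplies doses for use that Appendix III excludes. This is a contradiction in the text, in the period the protocol marks as carrying added tumor lysis risk, and it needs correcting. No assumption is required to see it.

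Three smaller points go with it: the inducer exception in Exclusion 17, which matters only if use continues on study; two posaconazole cells in Table 4, each 10 mg away from the other cells for the same unadjusted dose; and the missing cohort -1 ramp-up in Table 1. The two-cell finding rests on pairing Table 4 with Table 1 by cohort and day, and it shows a mismatch without showing which figure is intended.

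That sites would act differently, or that the MTD would be affected, is a reasonable inference from the small dose levels. The documents give no basis for putting a size on it.

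**What to change.** By protocol amendment:

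1. Reconcile Exclusion 17, Section 5.8.2, Table 4 and Appendix III so that one rule per drug class (strong inhibitors, moderate inhibitors, inducers) governs ramp-up and steady dose, in the same terms everywhere.
2. State whether the physician exception in Exclusion 17 is meant to reach inducers and, if so, how it fits with the exclusion in Appendix III for a patient who still needs one.
3. Have the sponsor verify the posaconazole cells for cohort 1 D0 and cohort 2 D0 against Table 1, and either correct them or note why they differ.
4. Reconcile Table 1 and the Section 5.4 text with Table 4 for cohort -1.

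Which rule and which doses apply is for the sponsor to decide. The cost is protocol wording and one table check; no extra patients or procedures are needed.
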